#### 16.1.10.9. Malignancies

Malignancies are those events recorded in BlcMQ "Malignancies" (narrow and broad) (refer to APPENDIX 5).

Number of subjects, percentages, number of events and patient-year incidence rate of Treatment Emergent Malignancies by SOC and PT tables will be prepared.

Malignancies will be listed.

#### 16.1.10.10. Chronic heart failure

Chronic heart failure are those events recorded in SMQ "Cardiac failure" (narrow).

Number of subjects, percentages, number of events and patient-year incidence rate of Treatment Emergent Chronic heart failure by SOC and PT tables will be prepared.

Chronic heart failure will be listed.

## 16.2. DEATHS

If any patients die during the trial as recorded on the completion or safety follow-up page of eCRF, the information will be summarized and listed.

## 16.3. LABORATORY EVALUATIONS

Results from the central laboratory will be included in the reporting of this trial for Serum Chemistry, Hematology and Urinalysis. A list of laboratory assessments to be included in the outputs is included in APPENDIX 4.

Presentations will use SI and US Units.

Quantitative laboratory measurements reported as "< X", i.e. below the lower limit of quantification (BLQ), or "> X", i.e. above the upper limit of quantification (ULQ), will be converted to X for the purpose of quantitative summaries, but will be presented as recorded, i.e. as "< X" or "> X" in the listings.

Qualitative laboratory urinalysis results measured by central laboratory will be classified to the categories "Positive" and "Negative" based on the central laboratory normal reference.

The handling of retests, unscheduled and end of trial measurements is described in Section 6.3. However, laboratory values taken after the first dose of trial medication up to a period of 10 weeks after the last dose of the trial medication will be assigned to the treatment phase for evaluation. All available data will be listed.

The following summaries will be provided for laboratory data:

- Actual and change from baseline in trial 1297.2 by visit (for quantitative measurements)

---

Document: \\ieedc-nas01a\BIOSdata\Boehringer\_Ingelheim\BI\_695501\NVA96235\Biostatistics\Documentation\SAP\10  
v1.0\BI\_1297.3\_SAP\_22JUN2016\_v1.0

Author: Version Number: 1.0  
Version Date: 22JUN2016

Template No: CS\_TP\_BS016 – Revision 3  
Effective Date: 01May2012

Reference: CS\_WI\_BS005

- Shifts in Rheumatology Common Toxicity Criteria (RCTC) grading, from baseline in trial 1297.2 by visit (for gradable parameters, see APPENDIX 4)
- Shifts from baseline category (Low/ Normal/ High) in trial 1297.2 by visit (for non-gradable parameters except urinalysis parameters and ADA)
- Shift from baseline category (Negative/ Positive) in trial 1297.2 by visit (for urinalysis non-gradable parameters)
- Box plots for ESR, CRP, hemoglobin, leukocytes (equivalent to white blood cells), platelets, AST, ALT, bilirubin, creatinine, cholesterol
- Plots for time course of gradable safety parameters for subjects having at least one value with toxicity grade 3 or 4 (RCTC grading is described section 16.3.3)
- Proportion and frequency of possible Hy's law subjects
- Proportion and frequency of possible Drug Induced Liver Injuries
- The time course of ALT, AST and total bilirubin (TBL) for all possible Hy's law subjects, all parameters shown on a logarithm to base 10 scale of the multiple of the upper limit of normal (ULN) (Y axis) versus days since treatment start (X axis).
- Scatter plots for Evaluation of Potentially Drug-Induced Liver Injury:
  1. log ALT on the X axis and log TBL on the Y axis, both shown on a logarithm to base 10 scale of the multiple of the ULN
  2. log AST on the X axis and log TBL on the Y axis, both shown on a logarithm to base 10 scale of the multiple of the ULN.

Baseline is described in Section 6.2.

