#### **7.3.4 Safety analyses**

Adverse events will be coded using the MedDRA coding dictionary. Standard BI summary tables and listings will be produced. All AEs with an onset between start of treatment and end of the residual effect period (REP), a period of 10 weeks after the last dose of trial medication, will be assigned to the treatment period for evaluation.

All treated patients will be included in the safety analysis. In general, safety analyses will be descriptive in nature and will be presented by MedDRA system organ class and preferred term. No hypothesis testing is planned.

Statistical analysis and reporting of AEs will concentrate on treatment-emergent AEs. To this end, all AEs occurring between start of treatment and end of the REP will be considered 'treatment-emergent'. Adverse events that start before first drug intake and deteriorate under treatment will also be considered as 'treatment-emergent'.

Frequency, severity, and causal relationship of AEs will be tabulated by system organ class and preferred term after coding according to the current version of the MedDRA.

In addition, for infections/serious infections, hypersensitivity reactions, drug-induced liver injury (DILI) and injection-site reactions, patient incidence and/or event incidence per 1000 patient-years exposure will be displayed.

Laboratory values taken after the first dose of trial medication up to a period of 10 weeks after the last dose of the trial medication will be assigned to the treatment phase for evaluation. Laboratory data will be analyzed both quantitatively as well as qualitatively. The latter will be done via comparison of laboratory data to their reference ranges. Values outside the reference range as well as values defined as clinically relevant will be highlighted in the listings. Treatment groups will be compared descriptively with regard to distribution parameters as well as with regard to frequency and percentage of patients with abnormal values or clinically relevant abnormal values.

Vital signs (blood pressure, pulse rate, respiratory rate and body temperature), physical examinations, 12-lead ECGs, or other safety-relevant data observed at screening, baseline, during the course of the trial and at the end-of-trial evaluation will be assessed with regard to possible changes compared to findings before start of treatment.

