### **16.3.3. RCTC GRADING FOR LABORATORY DATA**

Laboratory results will be classified according to the Rheumatology Common Toxicity Criteria v.2.0.

Only programmable parts of definitions will be performed.

The "Grade 0" will be introduced to indicate that a certain laboratory value can be seen as "normal" and does not fulfill the criteria of RCTC grading. For uncertain cases (for example when the values can be assigned to grade 0 based on the normal range and grade 1 or 2 based on the toxicity criteria), a medical check will be performed, to determine the correct grade.

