## APPENDIX 4. LABORATORY ASSESSMENTS

Laboratory parameter	Gradable with RCTC	US unit	SI unit
Serum chemistry			
Creatinine	X	mg/dL	umol/L
Alkaline phosphatase	X	U/L	U/L
Aspartate aminotransferase (AST)	X	U/L	U/L
Alanine aminotransferase (ALT)	X	U/L	U/L
Gamma glutamyl transpeptidase (GGT)		U/L	U/L
Total bilirubin	X	mg/dL	umol/L
Direct bilirubin	X	mg/dL	umol/L
Glucose	X (Hypoglycemia)	mg/dL	mmol/L
Total cholesterol		mg/dL	mmol/L
Total protein		g/dL	g/L
Albumin		g/dL	g/L
Sodium	X (Hyponatremia)	mEq/L	mmol/L
Potassium	X (Hypokalemia/Hyperkalemia)	mEq/L	mmol/L
Chloride		mEq/L	mmol/L
Calcium	X Hypocalcemia/Hypercalcemia	mg/dL	mmol/L
Hematology			
Hemoglobin	X	g/dL	g/L
Hematocrit		%	V/V
Platelets	X	10^3/uL	10^9/L
White blood cells	X	10^3/uL	10^9/L
Lymphocytes	X	10^3/uL	10^9/L
Neutrophils	X	10^3/uL	10^9/L
Urinalysis			
Protein		g/dL	g/L
Glucose		mg/dL	mmol/L
Blood		N/A	N/A

Document: \\ieedc-nas01a\BIOSdata\Boehringer\_Ingelheim\BI\_695501\NVA96235\Biostatistics\Documentation\SAP\10  
 v1.0\BI\_1297.3\_SAP\_22JUN2016\_v1.0

Author: Version Number: 1.0  
 Version Date: 22JUN2016

Template No: CS\_TP\_BS016 – Revision 3  
 Effective Date: 01May2012

Reference: CS\_WI\_BS005

---

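### A new high serum glucose or sodium shows as High in no planned shift table, so the reference-range patient counts promised in the protocol are missing for that direction

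*SAP*

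**What the plan says.** SAP 16.3 plans two kinds of shift table for blood parameters, both from the Trial 1297.2 baseline and by visit.

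- For gradable parameters: "Shifts in Rheumatology Common Toxicity Criteria (RCTC) grading, from baseline in trial 1297.2 by visit (for gradable parameters, see APPENDIX 4".
- For the others: "Shifts from baseline category (Low/ Normal/ High) in trial 1297.2 by visit (for non-gradable parameters except urinalysis parameters and ADA".

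Appendix 4 says which parameters are gradable and, for four of them, in which direction. Serum glucose carries the note "Hypoglycemia" and sodium the note "Hyponatremia". Potassium and calcium each name both the low and the high condition.

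SAP 16.3.3 adds a Grade 0, which "will be introduced to indicate that a certain laboratory value can be seen as" normal and which meets no RCTC criterion. SAP 16.3.2 derives Low, Normal and High for quantitative laboratory measurements in general.

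Protocol 7.3.4 provides for a qualitative laboratory analysis against reference ranges, with groups compared on "frequency and percentage of patients with abnormal values or clinically relevant abnormal values". SAP 3.3 states that no analysis departs from the protocol.

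**The concern.** The two lists are mutually exclusive at the level of the parameter, but RCTC grading as annotated in Appendix 4 is not always two-sided. A parameter graded only downward counts as gradable and so loses the Low/Normal/High table, yet its grades say nothing about the upper side.

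At stake is a categorical safety count in a trial whose primary purpose is safety. A reader of the shift tables could not tell how many patients moved from a normal to a high serum glucose or sodium in any of the three prior-treatment groups. A raised glucose is not a remote finding here, since Protocol Table 4.2.2.1: 1 allows oral corticosteroids up to 10 mg/day prednisolone or equivalent.

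**Working it through.** The plan states no figure to reproduce. The check is a count from Appendix 4, followed by tracing a high value through the planned displays.

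**Step 1: which table each parameter gets (Appendix 4 and SAP 16.3).**

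| | Parameters | Marked gradable (grade shifts) | Not marked (Low/Normal/High shifts) |
|---|---|---|---|
| Serum chemistry | 15 | 10 | 15 − 10 = 5 |
| Haematology | 6 | 5 | 6 − 5 = 1 |
| Total | 21 | 15 | 6 |

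The six are gamma glutamyl transpeptidase, total cholesterol, total protein, albumin, chloride and haematocrit.

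**Step 2: direction notes among the 15 gradable parameters.** Four carry a note: potassium and calcium in both directions, glucose and sodium in the low direction only. The other 15 − 4 = 11 carry none. Because the same table annotates potassium and calcium both ways, the one-sided notes read as deliberate. The gap is therefore shown for two parameters.

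**Step 3: trace a new high serum glucose or sodium through the planned displays.**

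| Display | What it shows |
|---|---|
| RCTC grade shift | Parameter included, but only its low side is graded |
| Low/Normal/High shift | Parameter excluded because it is marked gradable |
| Urinalysis Negative/Positive shift | Urine glucose only, a different measurement |
| Box plots | Ten named parameters; neither glucose nor sodium among them |
| Time-course plots | Need a grade 3 or 4 value, which an ungraded direction cannot produce |
| By-visit actual values and changes | Values included, with the maximum (SAP Appendix 1), but no patient count |
| Listings | Individual values, highlighted when out of range (Protocol 7.3.4), but no count |
| Adverse event tables | Counted per patient if judged clinically significant and reported |

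The number of shift tables that can show a move to High is 0 for glucose and 0 for sodium.

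**Step 4: the grade such a value would receive.** Grade 0 in SAP 16.3.3 has two conditions: the value can be regarded as normal, and it meets no RCTC criterion. A value above the reference range in an ungraded direction meets the second and fails the first. No other grade applies, so the SAP leaves the case undefined. The medical check in 16.3.3 is for uncertain cases. Its example is the reverse situation (inside the normal range but graded by the toxicity criteria), and what it yields is a grade, not a High category.

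**Step 5: compare with the protocol.** Protocol 7.3.4 calls for comparison with reference ranges and for patient counts of abnormal values, and names no parameter or direction to leave out. SAP 16.3 plans no such count for high glucose or high sodium, although SAP 16.3.2 already derives the category. SAP 3.3 does not declare the omission.

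**The case against.** The strongest reply is that little is hidden.

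- **Adverse events.** Protocol 5.3.3 makes a clinically significant laboratory abnormality an adverse event, apart from values consistent with a current diagnosis, and Protocol 5.3.7 repeats the requirement for clinically relevant changes. SAP 16.1.2 tabulates all treatment-emergent events with numbers of patients. This stands: the values that matter most would normally be counted there. What remains uncounted is out-of-range values not reported as events, which a reference-range table is designed to capture without relying on individual judgement.
- **Other displays.** Summaries include maxima, and listings highlight out-of-range values. This also stands, but neither gives the number of patients affected.
- **Protocol wording.** Protocol 7.3.4 joins abnormal and clinically relevant abnormal values with an or, and prescribes no shift table. The format is indeed open. Even so, the section calls for comparison with reference ranges, and SAP 16.3 plans no count of that kind for this direction.
- **Interpretation.** Protocol 5.3.3 does not specify fasting for routine glucose, so a count of High values would need care. That limits what the count means; it does not justify leaving it out.
- **Unseen sources.** The RCTC text and the output templates cited in SAP section 8 were not available. The templates might contain an abnormality count, in which case the SAP text should say so.

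A reader might infer that the plan reports a high glucose as normal, for instance as a Grade 0 to Grade 0 shift. The documents do not support this, because Grade 0 requires the value to be regarded as normal; the plan is silent on the case. Nor do they support saying that high values drop out of every patient count, given the adverse event tables.

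**Conclusion.** The point holds for serum glucose and sodium in the high direction. Under SAP 16.3 as written, no planned shift table shows a move to High for either, 16.3.3 leaves the grade undefined, and the count promised in Protocol 7.3.4 is not planned, with no change declared. This rests on reading the Appendix 4 notes as the full extent of grading for these two parameters.

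The size is 2 of 21 chemistry and haematology parameters, one direction each. It would be tempting to cite all 15 gradable parameters that lack a Low/Normal/High table, but that is not the size of the gap: potassium and calcium are graded both ways, and for the other 11, including haemoglobin, platelets and the white-cell counts, Appendix 4 gives no direction, so the documents do not show whether a gap exists. They also give no rate of high glucose or sodium, so no number of affected patients can be stated.

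This is a gap in categorical safety reporting, not a loss of data. It does not touch the primary endpoint's definition. It is worth closing because the derivation already exists and the correction is small.

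**What to change.** In SAP 16.3, produce the existing Low/Normal/High shift table for serum glucose and sodium in addition to their RCTC shifts. That raises its coverage from 6 to 6 + 2 = 8 parameters. The simplest wording extends it to all 21 quantitative chemistry and haematology parameters, which also removes any doubt about those without a direction note.

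In SAP 16.3.3, state that Grade 0 is not assigned to a value outside the reference range in an ungraded direction, and that such values are shown as 'not gradable - High' or 'not gradable - Low'.

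The cost is a wording change and extra runs of a table already planned. The categories come from SAP 16.3.2, so no new data or derivation is needed. The downside is a few more tables.

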### 16.3.1. LABORATORY SPECIFIC DERIVATIONS

- Log ALT = logarithm to base 10 scale of the multiple of the ULN of ALT
- Log AST = logarithm to base 10 scale of the multiple of the ULN of AST
- Log TBL = logarithm to base 10 scale of the multiple of the ULN of TBL. Note: Bilirubin value instead of TBL will be used.
- Potential Hy's law categories:

Document:	\\ieedc-nas01a\BIOSdata\Boehringer_Ingelheim\BI_695501\NVA96235\Biostatistics\Documentation\SAP\10\v1.0\BI_1297.3_SAP_22JUN2016_v1.0	Version Number:	1.0
Author:		Version Date:	22JUN2016

Template No: CS\_TP\_BS016 – Revision 3  
Effective Date: 01May2012

Reference: CS\_WI\_BS005

1. Category 1: ALT or AST  $\geq 3 \times \text{ULN}$  and TBL  $\geq 2 \times \text{ULN}$  within the same sample
2. Category 2: TBL  $\geq 2 \times \text{ULN}$  within 30 days after transaminase peak ( ALT or AST  $\geq 3 \times \text{ULN}$  )

- Potential Hy's Law subjects are defined as subjects with laboratory data in at least one Potential Hy's law categories at any time point of the trial.
- Drug induced liver injury :
  1. Category 1 : AST and/or ALT  $\geq 3$  times ULN and TBL  $\geq 2$  times ULN within the same sample
  2. Category 2: AST and/or ALT  $\geq 3$  times the Baseline value and TBL  $\geq 2$  times the Baseline value within the same sample.
  3. Category 3 : marked peak aminotransferase (ALT, and/or AST) elevations  $\geq 10$  fold ULN

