13. Current inflammatory joint disease other than RA (e.g., gout, reactive arthritis, psoriatic arthritis, seronegative spondyloarthropathy, Lyme disease) or other systemic autoimmune disorder (e.g., systemic lupus erythematosus, inflammatory bowel disease, pulmonary fibrosis, or Felty's syndrome, scleroderma, inflammatory myopathy, mixed connective tissue disease, or any overlap syndrome). Secondary Sjögren's syndrome or secondary limited cutaneous vasculitis with RA is permitted.
14. Any planned surgical procedure, including bone/joint surgery/synovectomy (including joint fusion or replacement) for the duration of the trial.
15. Known active infection of any kind (excluding fungal infections of nail beds), or any major episode of infection requiring hospitalization or treatment with intravenous (i.v.) anti-infectives within 4 weeks of the Screening Visit or completion of oral anti-infectives within 2 weeks of the Screening Visit.
16. Serious infection or opportunistic infection during the 1297.2 trial.
17. Any acquired neurological, vascular, systemic or demyelinating disorder that might affect any of the efficacy assessments, in particular, joint pain and swelling (e.g., Parkinson's disease, cerebral palsy, diabetic neuropathy) that occurred during the 1297.2 trial.
18. Currently active alcohol or drug abuse.

19. Treatment with i.v. Gamma Globulin or the ProSORBA® Column during the 1297.2 trial.
20. Planned treatment with i.v. intramuscular, intra-articular and parenteral corticosteroids.
21. Aspartate aminotransferase (AST) or alanine aminotransferase (ALT) >1.5 times upper limit of normal (ULN).
22. Hemoglobin <8.0 g/dL.
23. Platelets <100,000/ $\mu$ L.
24. Leukocyte count <4000/ $\mu$ L.
25. Creatinine clearance <60 mL/min.
26. Patients who are currently participating in another clinical trial other than Trial 1297.2.

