### **Adverse events of special interest (AESIs)**

The term AESI relates to any specific AE that has been identified at the project level as being of particular concern for prospective safety monitoring and safety assessment within this trial, e.g., the potential for AEs based on knowledge from other compounds in the same class. AESIs need to be reported to the Sponsor’s/Sponsor’s designee Pharmacovigilance Department within the same timeframe that applies to SAEs, see [Section 5.3.7](#).

The following are considered as AESIs:

- Hepatic injury

A hepatic injury is defined by the following alterations of hepatic laboratory parameters:

- An elevation of AST and/or ALT  $\geq 3$  fold ULN combined with an elevation of total bilirubin  $\geq 2$  fold ULN measured in the same blood draw sample, and/or
- Marked peak aminotransferase (ALT, and/or AST) elevations  $\geq 10$  fold ULN

These laboratory findings constitute a hepatic injury alert and the patients showing these laboratory abnormalities need to be followed up according to the “DILI checklist” provided in the ISF.

In case of clinical symptoms of hepatic injury (icterus, unexplained encephalopathy, unexplained coagulopathy, right upper quadrant abdominal pain, etc.) without laboratory results (ALT, AST, total bilirubin) available, the Investigator should make sure these parameters are analyzed, if necessary in an unscheduled blood test. Should the results meet the criteria of hepatic injury alert, the procedures described in the DILI checklist should be followed.

- Anaphylactic reactions
- Serious infection (defined as infections requiring i.v. antibiotics or meeting the regulatory definition of a SAE)
- Hypersensitivity reactions.

Protocol-specified AESIs can be classified as serious or nonserious, but all AESIs must be reported in an expedited manner similar to SAEs on an SAE form (i.e., nonserious AESIs must be reported on the SAE form and follow SAE reporting timelines).

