### 3.3. CHANGES TO ANALYSIS FROM PROTOCOL

No change is planned.

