#### **16.1.7.4. Drug Induced Liver Injury (DILI)**

Drug Induced Liver Injury (DILI) are those events identified by medical advisor on the subset of AEs for subjects presenting laboratory potential DILI findings (refer to section 16.3).

DILI events of special interest are those events both identified as DILI adverse events and recorded as "Adverse Event of Special Interest" equal to "Yes" on the Adverse Events page of the eCRF.

---

Document:	\ieedc-nas01a\BIOSdata\Boehringer_Ingelheim\BI_695501\NVA96235\Biostatistics\Documentation\SAP\10\		
Author:		Version Number:	1.0

Template No: CS\_TP\_BS016 – Revision 3  
Effective Date: 01May2012

Reference: CS\_WI\_BS005

Copyright © 2012 . All rights reserved.  
The contents of this document are confidential and proprietary to . Unauthorized use, disclosure or  
reproduction is strictly prohibited.

Treatment Emergent DILI will be tabulated separately.

Drug Induced Liver Injury (DILI) will be listed.

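### SAP DILI category 2 uses multiples of the patient's own baseline with no ULN condition, is absent from the protocol's hepatic-injury definition and is undeclared, so samples within the reference range can count as possible DILI

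*SAP*

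**What the plan says.** Protocol 5.3.6, under adverse events of special interest, introduces its criteria with "A hepatic injury is defined by the following alterations of hepatic laboratory parameters". There are two. The first is AST and/or ALT at least 3 "fold ULN combined with an elevation of total bilirubin" at least 2 times ULN in the same blood draw. The second is ALT and/or AST at least 10 times ULN. Neither refers to the patient's baseline.

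SAP 16.3.1 defines drug-induced liver injury by three categories:

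- Category 1: AST and/or ALT at least 3 and total bilirubin (TBL) at least 2 "times ULN within the same sample".
- Category 2: AST and/or ALT at least 3 and TBL at least 2 "times the Baseline value within the same sample".
- Category 3: "marked peak aminotransferase (ALT, and/or AST) elevations" of at least 10 times ULN.

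SAP 16.3 lists the proportion and frequency of possible DILI among its laboratory summaries. SAP 16.1.7.4 defines DILI adverse events as those "identified by medical advisor on the subset of AEs for subjects presenting laboratory potential DILI findings". SAP 16 lists the proportion of patients with DILI as a safety endpoint other than the primary. On departures from the protocol, SAP 3.3 says "No change is planned".

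**The concern.** Categories 1 and 3 are the protocol's two criteria. Category 2 is an addition on a different scale, and nothing in it requires a value to be abnormal. A patient with low-normal baseline values could therefore be counted as possible DILI on a sample that SAP 16.3.2 would classify as normal for both tests.

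Two outputs are exposed. The laboratory table of possible DILI takes the categories directly, with no adjudication described. The same laboratory findings also decide whose adverse events the medical advisor screens for DILI. Protocol 2.3 describes DILI as rare, so a few flags that do not meet the protocol definition could be a large share of a small count.

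Category 2 also does not say which baseline it multiplies. SAP 6.2 gives a 1297.3 default (last value before the first extension dose) and also says endpoints use the 1297.2 baseline. The other laboratory summaries in SAP 16.3 use 1297.2, and that section then refers back to 6.2. The choice can change who is flagged.

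**Working it through.** The documents give no figure for this point, so there is none to reproduce. The check has three steps: threshold algebra, worked examples, and an illustrative simulation.

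**1. Thresholds in multiples of ULN.** Let a and t be the on-treatment transaminase and TBL, and bA and bT the baselines, all divided by ULN.

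- Category 1: a ≥ 3 and t ≥ 2.
- Category 2: a ≥ 3·bA and t ≥ 2·bT.
- Category 3: a ≥ 10.
- Protocol hepatic injury: category 1 or category 3.

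SAP 16.3.2 counts a value equal to the upper limit as normal. Category 2 can therefore be met inside the reference range when 3·bA ≤ 1 and 2·bT ≤ 1, that is, bA ≤ 1/3 and bT ≤ 1/2.

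| Baseline ALT or AST (× ULN) | Category 2 cut-off (× ULN) | Baseline TBL (× ULN) | Category 2 cut-off (× ULN) |
|---|---|---|---|
| 0.20 | 0.60 | 0.20 | 0.40 |
| 0.25 | 0.75 | 0.30 | 0.60 |
| 0.30 | 0.90 | 0.40 | 0.80 |
| 1/3 | 1.00 | 0.50 | 1.00 |

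If instead bA ≥ 1 (for the transaminase that meets the rule) and bT ≥ 1, then 3·bA ≥ 3 and 2·bT ≥ 2, so category 2 lies inside category 1 and adds nothing. Each added case therefore has at least one baseline value below ULN. Because categories 1 and 3 are the protocol definition, each added case also falls short of it.

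**2. Examples.** Assumed ULNs, not in the documents: ALT 40 U/L, TBL 1.2 mg/dL.

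- ALT 12 to 36 U/L: bA = 12/40 = 0.30, cut-off 0.90, a = 36/40 = 0.90. TBL 0.4 to 0.8 mg/dL: bT = 0.33, cut-off 0.67, t = 0.67. Category 2 is met; categories 1 and 3 are not.
- ALT 10 to 32 U/L: bA = 0.25, cut-off 0.75, a = 0.80. TBL 0.3 to 0.7 mg/dL: bT = 0.25, cut-off 0.50, t = 0.58. Same result.
- bA = 1.5, bT = 1.0, a = 4.6, t = 2.1: cut-offs 4.5 and 2.0. Category 2 is met, but so is category 1.

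**3. Illustrative count.** The documents give neither a baseline distribution nor within-patient variation, so every input here is an assumption except the four post-dose samples (Weeks 12, 24, 48 and 58 in the Flow Chart) and the 350 patients, the midpoint of the anticipated 300 to 400. Assumed: no drug effect; independent log-normal ALT (median 20 U/L, between-patient log-SD 0.40) and TBL (median 0.5 mg/dL, log-SD 0.35); one baseline sample; ALT only; ULNs as in step 2.

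| Within-patient CV, ALT / TBL | Patients flagged by category 2 | Per 350 | Of these, wholly normal, per 350 |
|---|---|---|---|
| 25% / 25% | 0.008% | 0.03 | 0.01 |
| 35% / 30% | 0.20% | 0.7 | 0.3 |
| 45% / 35% | 0.97% | 3.4 | 1.45 |

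Roughly half of the flags or fewer are wholly normal. The rest have at least one value above ULN. One flagged patient is 1/350 = 0.29% of the trial.

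**The case against.** The case for leaving the rule alone has several sound parts.

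- **The protocol definition serves reporting.** Protocol 5.3.6 defines hepatic injury to trigger expedited reporting and follow-up, and the SAP does not alter that trigger. Protocol 7.3.4 names DILI as an analysis topic without a laboratory definition. This stands: category 2 is an undeclared addition to an analysis flag and does not change safety reporting. But SAP 16.1.10 does label its further selected adverse events as outside the protocol, and category 2 carries no such label.
- **Review follows the flag.** A DILI adverse event needs an adverse event that the medical advisor identifies. A sensitive screen followed by review is a legitimate design. This stands for the adverse-event endpoint but not for the laboratory proportion.
- **ULN-based results appear elsewhere.** The Hy's law categories and the scatter plots use ULN multiples. This stands, though a normal category 2 case would then be counted in the table and look normal in the plot.
- **Little depends on the count.** The trial is single-arm and descriptive, with no hypothesis test. This stands and limits the weight of the point.

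Three stronger readings are tempting and are not supported. A reader might infer that the three categories are pooled into one figure. The SAP gives no combining rule for DILI and leaves table content to templates outside these documents, so the rows may already be separate. A reader might also infer that the rule is pointless because patients with high baseline transaminases are barred. Exclusion criterion 21 admits values up to 1.5 times ULN, while footnote 8 of the Flow Chart gives 3 times ULN at baseline (the two must be reconciled). In any case an added category could not help patients whose baselines are both at or above ULN, by the containment in step 1. Finally, a reader might take all category 2 flags as normal values, which the simulation does not bear out.

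**Conclusion.** The point holds as a definition and labelling fault of modest size. Category 2 has no ULN condition, is not in the protocol's hepatic-injury definition, is not declared in SAP 3.3, and does not name its baseline. Following the plan as written can put samples that are normal on both tests into the possible-DILI count and into the pool for advisor review.

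The threshold results are exact and need no assumption. The size cannot be computed from the documents. The illustrative range of about 0.03 to 3.4 flags per 350 patients, with about 0.01 to 1.5 wholly normal, rests on the assumed medians, variation, ULNs and independence of ALT and TBL, and it leaves out AST, which could add flags. Two of the three scenarios give fewer than one flag, so the effect may be nil. The documents do not support a claim that the DILI adverse-event endpoint or the Hy's law outputs are distorted.

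**What to change.** - In SAP 16.3 and 16.3.1, define the possible-DILI proportion as the protocol-defined count: patients meeting category 1 or category 3.
- Show category 2 only on a separate row labelled exploratory. Name its baseline (1297.2 or 1297.3) and show how many flagged subjects had a transaminase above ULN in that sample. This keeps the sensitive screen and lets the reader see how much of it is abnormal, without imposing a floor that the documents do not give.
- Record the addition of category 2 in SAP 3.3.

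The cost is SAP wording and one extra table row. No new data are needed.
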